2.3 Potential Risks & Benefits

2.3.1 Known Potential Risks

Submaximal exercise testing. The 6-minute walk test (6MWT) is a submaximal exercise test in which the pace is self-selected by the participant. Theoretical risks include hypotension (drop in systolic BP ≥ 15 mmHg), angina, arrhythmia, dyspnea, leg cramps, and falls. For purposes of our study, we have operationalized the definition of IHD as either acute myocardial infarction (AMI), percutaneous coronary intervention (PCI), or coronary artery bypass graft (CABG); the AMI group (which in practice, may undergo PCI or CABG) is theoretically at higher risk during 6MWT. Patients undergoing elective PCI or elective CABG (by definition, not with AMI) are at lower risk, since they have not experienced an acute ischemic event. While guidance from the American Thoracic Society published 15 years ago and often cited for instructions on performing the test⁵² recommended against performing submaximal exercise testing within 1 month of AMI, guidance from the American College of Cardiology and American Heart Association stated that such testing was acceptable prior to hospital discharge.¹¹³ Multiple subsequent studies have shown that events during 6MWT in patients hospitalized for IHD-related sequelae (including AMI) are rare in practice. Peixoto and colleagues reported that among 88 patients with AMI who completed 6MWT prior to hospital discharge, there were no adverse events.⁶² Oliveira performed 6MWT on 60 patients who underwent cardiac surgery (including CABG for IHD) prior to discharge, and reported that all participants successfully completed the test with no adverse events.⁶¹ In a more recent study, Diniz et al. performed 6MWT in 152 patients with AMI prior to discharge, and found that 3.9% of patients experienced either angina, hypotension, or arrhythmia (ventricular tachycardia), although all of these resolved upon cessation of the test.¹¹⁴ Understandably in these studies there may have been a selection bias whereby more acutely ill patients were excluded from enrollment.

Accordingly, for our study, patients may be excluded from participation by their treating physician on any clinical grounds which the physician deems would potentially lead to safety issues. Study entry criteria to exclude potential participants at greater risk of adverse events, including conditions at increased fall risk (Parkinson's disease or other progressive neurologic movement disorder, severe osteoarthritis, recent orthopedic surgery). In addition, since the baseline 6MWT will be performed in the hospital, emergency equipment and personnel are readily available to deal with unusual situations should they arise.

Home-based cardiac rehabilitation. Theoretical risks of home-based cardiac rehabilitation involve risks

CONFIDENTIAL

This material is the property of the NYU School of Medicine and Langone Medical Center. Do not disclose or use except as authorized in writing by the study sponsor

attributable to study-related exercise, which may occur at any point during the 3-month intervention period. We have defined major adverse events as the following: (1) Fall-related injury (operationalized as any fall requiring acute medical care); (2) Hospitalization for acute coronary syndrome (symptom onset within 30 minutes of exercise); (3) Hospitalization for unstable arrhythmia (symptom onset within 30 minutes of exercise). Based on decades of research on home-based CR interventions, adverse events are rare. Ades et al. reported that out of 3100 home-based rehab sessions, 7 sessions (0.2%) were canceled for symptoms (low-level angina, dyspnea, or arrhythmia), although none of these led to serious adverse consequences.⁷⁴ Jolly et al. reported zero adverse events in 263 participants for the duration of a 3-month home-based cardiac rehabilitation program.⁷³ Nonetheless, we understand the importance of active surveillance for potential study related adverse events in our enrolled participants, especially given that by definition we are limiting our sample to older adults (age ≥ 65).

To minimize risk, all procedures will be performed in clinically stable participants who meet eligibility criteria under the direct supervision of the Principal Investigator and other research personnel with appropriate training and licensure. The baseline visit will be performed in-hospital, and the 3-month follow-up visit will be performed in dedicated space adjacent to the outpatient cardiology Faculty Group Practice, on the main campus of NYU Langone Health ([name]). For NYULH-Winthrop participants, this will be at the outpatient office of the FGP of Winthrop Cardiology Associates located at [name]. For UMMHC participants, this will be at the Ambulatory Care Center (1st floor) located at [name]. For participants at the Bellevue site, the CTSI Bellevue research suites or designated areas in the NYU main hospital campus will be used. For Yale participants, this will be at outpatient ambulatory space adjacent to Yale-New Haven Hospital (hospital address: [name]). All locations have immediate access to emergency support equipment and personnel in the event of deterioration in clinical status. Participants with severe cardiac symptoms during baseline assessment (6MWT) that would place them at potentially increased risk for adverse events with home-based exercise (e.g. hypotension (drop in systolic BP ≥ 15 mmHg), severe angina, unstable arrhythmia) will not undergo randomization, and the DSMB will be notified. In addition, participants with severe orthopedic complaints during 6MWT (e.g. intolerable back pain due to spinal stenosis), who need to stop walking entirely before the test is completed because of this pain, will not undergo randomization. These events will constitute a "screen failure."

Confidentiality. As with any study that collects patient-level data, there is the potential for a breach of confidentiality due to unintentional release of research records.

For our study, all patient data will be kept strictly confidential, except when published for purposes of reporting data. In that case, the patients are never identified. All electronic data will be de-identified and transmitted and stored with secure systems that meet or exceed Federal guidelines. The Principal Investigator will maintain files with identifying information in a locked cabinet in a locked room or in password-protected files on a password-protected computer. Since IHD is a common condition and the study is being conducted in a densely populated area, it is extremely unlikely that participants could be identified from an anonymized dataset.

Financial incentives. Low-income participants (e.g. Medicaid beneficiaries) may be vulnerable to financial incentives to enroll in the research study. We will therefore delineate in the informed consent that compensation should not be the sole grounds for participation in the research project and should not cause participants to assume risks that they would not ordinarily find acceptable. We designed study compensation to be modest in order to not unduly influence participation. Simultaneously, we will also aim to ensure that participants do not incur additional costs from the study that may be burdensome. We have therefore built in transportation costs for the 3-month follow-up assessment visit. In addition, study equipment will be provided to participants at no charge, and a toll-free number will be provided to reach the research coordinator for ongoing communication as necessary. There are no anticipated out-of-pocket costs for participants using the mobile health software application. A home WiFi network is not required. Tablet devices will have cellular capability, provided by the study.

2.3.2 Known Potential Benefits

There is no definitive direct benefit to participants from study treatment or other study procedures during the course of the study. If the mHealth-CR therapy turns out to be beneficial, then participants assigned to this study arm will benefit, although this will not be known until conclusion of the study.

CONFIDENTIAL

This material is the property of the NYU School of Medicine and Langone Medical Center. Do not disclose or use except as authorized in writing by the study sponsor

3 Objectives and Purpose

The study includes objectives relate to both efficacy and engagement.

3.1 Primary Objective

The *primary efficacy objective* is to determine whether mHealth-CR, in patients age ≥ 65 with ischemic heart disease (IHD), improves functional capacity as assessed by 6 Minute Walk Distance (6MWD), compared to usual care.

The *primary engagement objective* is to characterize engagement of participants with mHealth-CR and elucidate barriers to participation.

3.2 Secondary Objectives

The *secondary efficacy objectives* are to evaluate whether mHealth-CR improves the endpoints of (1) goal attainment, as measured by goal attainment scaling (GAS); (2) health status (general and disease-specific); (3) basic and instrumental activities of daily living (ADLs); (4) hospital readmission; and (5) death, in participants receiving mHealth-CR versus usual care.

The *ancillary efficacy objectives* are to assess whether mHealth-CR improves the quantitative endpoints of (1) mean systolic blood pressure at 3-month follow-up visit; (2) change in frailty status; (3) attendance rate at traditional (ambulatory) CR; (4) change in PHQ-8 depression score (baseline to 3 months).

4 Study Design and Endpoints

4.1 Description of Study Design

RESILIENT is a phase II, multicenter, prospective, 3:1 open-label pragmatic randomized clinical trial (with blinded assessment of primary endpoint). Participants with IHD will be identified at the time of acute myocardial infarction (AMI), percutaneous coronary intervention (PCI), or coronary artery bypass graft (CABG), and will be randomized in a 3:1 ratio to a mobile health cardiac rehabilitation program (mHealth-CR) in addition to usual care or to usual care alone for 3 months. Randomization will be stratified by institution (NYU-main campus, NYU-Winthrop, Bellevue Hospital, and UMMHC) to ensure balance across treatment arms given between-hospital population differences. We will randomize a total of 400 participants within the NYU School of Medicine / NYU Langone Health System, Bellevue Hospital, and UMMHC, which serve a diverse patient population in the New York City and Massachusetts. We plan to enroll a target of 200 participants within the NYU School of Medicine/ NYU Langone Health System, and 150 participants within UMMHC and 50 within Bellevue Hospital.

Study enrollment has been paused indefinitely at the Yale New Haven site. This site might contribute to enrollment again in the future.

4.2 Study Endpoints

4.2.1 Primary Study Endpoints

Primary Efficacy Endpoint. The primary endpoint of this study is the change in the 6MWD between the baseline visit and 3-month follow-up visit. Change in 6MWD, reflective of functional capacity, is measured by the 6-minute walk test (6MWT). The 6MWT will be performed during baseline hospitalization and at the 3-month follow-up visit by a blinded research nurse or exercise therapist.

Primary Engagement Endpoint. Our main measure of engagement is weekly percent completion of the mHealth-CR program. Completion of mHealth-CR analyzed at weekly intervals will allow us to determine distinct engagement trajectories over the 3-month study period. Weekly engagement will be measured as the fraction of the following 11 elements completed each week: (1–7) daily entry of exercise data and RPE; (8) completed weekly phone call with exercise therapist; (9) at least one electronic communication with exercise therapist; (10) watching educational video (which will vary by week); and (11) at least one home BP measurement. Engagement will be assessed as a pseudo-continuous outcome, as the score can range from 0% (0 activities

CONFIDENTIAL

This material is the property of the NYU School of Medicine and Langone Medical Center. Do not disclose or use except as authorized in writing by the study sponsor

completed) to 100% (all 11 activities completed). We will also explore determination of a threshold for minimally sufficient engagement that is associated with improved outcomes.

4.2.2 Secondary Study Endpoints

Protocol-defined secondary endpoints are: (1) goal attainment, as measured by goal attainment scaling (GAS); (2) change in participant reported health status: general (SF-12) and disease specific (SAQ-7); (3) change in activities of daily living (ADLs); (4) hospital readmission; and (5) death, in participants receiving mHealth-CR versus usual care.

- *Goal attainment*, defined as whether a person's individual functional goals are achieved as a result of the study intervention, will be measured using a 5-point goal attainment scale (GAS). Using the SMART goal framework,⁶³ GAS describes the person's expected level of goal achievement over 3 months, ranging from no change (scored as -2) to much better than expected (scored as +2). Scales are dynamically set according to a person's needs, while measurement of attainment is standardized. Goal attainment, through goal setting, is an especially important outcome in older adults who may begin an intervention with a variety of deficits (therefore necessitating individualized therapy towards realistic goals).⁶⁴
- *Participant reported health status* is measured using the SF-12⁶⁵ (general health status) and Seattle Angina Questionnaire 7 (SAQ-7)⁶⁶ (disease-specific health status). Health status encompasses a person's functional status, symptoms, and well-being, and is increasingly recognized as an important patient-centered outcome.^{67,68} Both the SF-12 and SAQ-7 have been validated and are convenient for participants (<5 minutes to administer). For the SF-12, we will analyze change from baseline to 3 months using a threshold of 5 points in SF-12 physical component score (PCS) as a clinically meaningful change.⁶⁹ For SAQ-7, we will analyze at a single time point (3 months) the number of participants who have residual angina (SAQ-7<100) vs. no angina (SAQ-7=100).⁶⁶
- *Change in ADLs* is defined as any improvement or worsening in basic (BADLs) or instrumental (IADLs) activities of daily living over 3 months. BADLs are basic self-care behaviors: feeding, toileting, bathing, dressing, and ambulating.⁷⁰ IADLs are activities that allow a person to live independently (e.g. food preparation, medication management, transportation, shopping, managing finances, using the telephone, and housekeeping).⁷⁰ ADL preservation is repeatedly cited by older adults as an important outcome,⁹ and prior research has shown that many patients with IHD experience ADL decline after hospitalization.⁷¹
- *Hospital readmission* is defined as an overnight stay (including observation) in any hospital within 3 months of discharge. Readmissions in older adults with IHD are common, costly, and disruptive; multiple entities within the U.S. healthcare system emphasize reducing potentially preventable readmissions.⁷² Since these data are obtainable via the electronic health record (EHR), we will also ascertain readmission events at 6 months and 1 year.
- *Death* is defined by death from any cause within 3 months of enrollment. Given our sample size, we do not expect to detect a significant difference in mortality rates, but a descriptive analysis may place other endpoints in context. In addition, absolute mortality rates can assist with planning of subsequent studies. Similar to readmission, we will also ascertain death at 6 months and 1 year through the EHR.

Safety Endpoint. The safety endpoint will be assessed at the 3-month ambulatory visit and includes (1) fall-related injury (operationalized as any fall requiring acute medical care); (2) hospitalization for acute coronary syndrome; and (3) hospitalization for unstable arrhythmia. Separately, among intervention participants, study staff will monitor potential exercise-related adverse events on an ongoing basis. Points of contact will include weekly phone calls with the exercise therapist as well as electronic communication via the mHealth app which is checked daily. All adverse events will be reported directly to the Principal Investigator and to the DSMB. In order to reduce the likelihood of these events, participants will complete the baseline 6MWT in-hospital; if any adverse event occurs during 6MWT (drop in SBP ≥ 15 mmHg, chest pain, ventricular arrhythmia), participants will be removed (not randomized). Other exclusion criteria (severe osteoarthritis, recent joint replacement,

CONFIDENTIAL

This material is the property of the NYU School of Medicine and Langone Medical Center. Do not disclose or use except as authorized in writing by the study sponsor

moderate or severe cognitive impairment) are also intended to minimize risk. Prior studies of home-based CR have reported that adverse events are uncommon.^{73,74}

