5.1 Inclusion Criteria

In order to be eligible to participate in this study, an individual must meet all of the following criteria:

1. Age ≥ 65 .
2. Currently hospitalized for AMI, PCI, or CABG **or**
Hospitalized for AMI, PCI or CABG within prior 4 weeks.
3. Capable of self-consent.
4. Understand and are able to perform study procedures (i.e. 6-minute walk test, use mHealth in English or Spanish).

Given logistical considerations, we expect that most participants with AMI and/or PCI will be recruited from the inpatient setting, with the baseline assessment taking place before discharge. However, given recent trends in AMI and PCI care (shorter hospital stays, including same-day discharge after PCI), we may not be able to capture all eligible participants at the time of hospitalization. In this case, the baseline study visit will take place at the first ambulatory cardiology visit (provided this occurs within 4 weeks of hospitalization). Since patients undergoing CABG have exposure to much greater physiologic stress as they recover from surgery, our expectation is that they will not be enrolled in the hospital (given inability to participate in mHealth-CR immediately after discharge), but instead will be enrolled at the first ambulatory visit (provided within 4 weeks of discharge). For patients with AMI or PCI, they can be enrolled either in the hospital or the first ambulatory visit (provided within 4 weeks of discharge).

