5.4 Strategies for Recruitment and Retention

Recruitment. Inclusion and exclusion criteria will be determined through screening of the EHR.

The research coordinator will screen the list of patients and send potentially eligible patients to the Principal Investigator for review. At the NYU site, [name], a clinically trained cardiologist, will be responsible for reviewing the list of eligible patients and whether inclusion/exclusion criteria are met. For those deemed eligible, the research team will send an email to the attending physician (usually a cardiologist) notifying that the study team will approach the patient for participation in the research study. [name] and [name] will be responsible at the NYU-Winthrop location for reviewing and confirming eligible patients identified by the NYU-Winthrop coordinator, while [name] will be responsible at the UMMHC site for reviewing and confirming eligible patients identified by the UMMHC research coordinator(s). [name] will be responsible at the Yale site for reviewing and confirming eligible patients identified by the Yale research coordinator(s).

CONFIDENTIAL

This material is the property of the NYU School of Medicine and Langone Medical Center. Do not disclose or use except as authorized in writing by the study sponsor

For eligible patients identified at Bellevue Hospital, the Research Coordinator will send a letter introducing the trial as well as the most current IRB-approved version of the informed consent form. Eligible patients will be called for approach after the letters are sent in order to allow patients to reference the informed consent form during the phone approach. This method will account for high rates of patients at Bellevue Hospital who do not or cannot use email for receipt of informed consent after a phone approach.

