Enrollment. For participants currently hospitalized for AMI, PCI, or CABG at the time of screening, participants will be approached in-person by the study team for potential enrollment in the study during a period of clinical stability in the inpatient setting (usually this is close to the time of hospital discharge). Participants who have been discharged from the hospital but are eligible due to recently diagnosed AMI, PCI, or CABG (within 4 weeks of the screening date) will receive a message through the EPIC electronic health record, introducing the participant to the study, and will have the option to “opt out” of being approached by replying to the message. If they do not opt out, they will be approached by the research coordinator for potential enrollment at the time of the next outpatient cardiology visit, provided this occurs within 4 weeks of AMI, PCI, or CABG. In the circumstance that it is not possible for the research coordinator to approach an eligible subject in-person in an inpatient setting, or within 4 weeks of discharge during an outpatient appointment, the research coordinator will call the eligible subject at the preferred phone number in their chart to introduce the study. Eligible patients will have the option of scheduling a research visit to undergo the informed consent process and to complete the baseline visit. For outpatients enrolled in the study, the baseline visit will take place in close proximity to dedicated ambulatory space at NYU Main Campus (Cardiology Faculty Group Practice), NYU Winthrop Campus (Winthrop Cardiology Associates), UMMHC (Ambulatory Care Center), or Yale-New Haven Health (Yale Cardiovascular Medicine, Outpatient Practice).

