Detail. Patients in the intervention group will receive an individualized exercise prescription including aerobic and strength training exercises. The CDC's Physical Activity Guidelines (PAG) goal of a minimum of 150 minutes per week of moderate intensity or 75 minutes per week of vigorous intensity exercise, including 2 days of muscle strengthening, will be used to develop the exercise prescription. The aerobic portion will be informed by the results of the six-minute walk test, while patients will also receive a general upper and lower body strength training program. The prescription will be reviewed with the patient during the therapy initial contact, either in person or remotely through Zoom video conference. As participants by definition are age ≥ 65 , and functional impairments may be present in this population, adjustments to these goals will be made as clinically indicated (e.g. reduced initial number of target minutes in a participant with mobility impairment). Initial contact will take place within 4 weeks of hospitalization for myocardial infarction or coronary revascularization procedure. When feasible, participants will be enrolled in-hospital, but given logistical concerns (e.g. same day discharge after PCI) there will be the potential for enrollment during the first outpatient follow-up visit. The exercise prescription will be monitored on weekly phone calls to ensure compliance and will determine if adjustments need to be made (described 6.1.1).

The exercise prescription and baseline cardiovascular fitness level will be determined from the six-minute walk test (6MWT) and initial therapy contact. Data collected during the 6MWT will include: resting and exertional vital signs, rate of perceived exertion (RPE), and distance walked (6MWD). The prescription will provide guidance on the frequency, intensity, type, and duration of an appropriate exercise session. Participants will be able to use established HR and RPE to achieve the desired exercise intensity. Participants will be provided suggestions for both aerobic and strength exercises.

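### The readmission window opens at hospital discharge, but some participants are randomised up to about four weeks later and are asked only about stays since baseline

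*Combined protocol and SAP*

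**What the plan says.** **Endpoint.** Section 4.2.2: hospital readmission "is defined as an overnight stay (including observation) in any hospital within 3 months of discharge". Readmissions are also to be ascertained from the EHR at 6 months and 1 year. Death, in the same section, is counted from enrollment.

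**Enrolment.** Under section 5.1 CABG patients are not expected to enrol in hospital but "instead will be enrolled at the first ambulatory visit (provided within 4 weeks of discharge". For AMI and PCI, "they can be enrolled either in the hospital or the first ambulatory visit (provided within 4 weeks of discharge". The same section limits how common this is: "we expect that most participants with AMI and/or PCI will be recruited from the inpatient setting". Other places start the 4 weeks earlier: section 5.4 has "provided this occurs within 4 weeks of AMI, PCI, or CABG" and section 7.1.1 has "Initial contact will take place within 4 weeks of hospitalization for myocardial infarction or coronary revascularization procedure". Section 7.1.1 places randomisation after consent and the baseline assessment.

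**Collection.** Section 7.1.1 sets the follow-up visit 3 months after baseline and asks about readmissions since the last visit. The only earlier scheduled visit is baseline, Day 1 (section 7.2.2). Section 7.2.4 allows the final visit from Day 90 to Day 120. Chart abstraction (Table 1: Week 8 and follow-up) is described as verifying what participants report.

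**Analysis.** Section 10.4.3 plans Kaplan-Meier, logrank and Cox analyses without naming a time zero. The power table in section 10.5 labels the endpoint only as admission by 3 months.

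**The concern.** For anyone randomised after discharge, the defined window opens before treatment assignment. Stays in that stretch occur at the same rate in both arms in expectation, so counting them pulls the arms together. Closing the window 90 days after discharge also omits an equal number of days at the end of the intervention.

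The data collection does not follow the definition either. The questionnaire does not ask about stays before baseline, yet it can pick up stays more than 3 months after it. If the analysis starts at discharge but early stays were never ascertained, late enrollees contribute time in which no event could be recorded. Two analysts working from these sections could count different events for the same participant.

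Only post-discharge enrollees are affected. For participants enrolled in hospital, randomisation precedes discharge and no part of the window comes before it.

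**Working it through.** **1. The two clocks, in days since discharge**

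| Randomised on day | Endpoint window | Part before randomisation | Questionnaire covers |
|---|---|---|---|
| 14 | 0-90 | 14/90 = 16% | 14-104 (to 134 at the latest visit) |
| 28 | 0-90 | 28/90 = 31% | 28-118 (to 148 at the latest visit) |

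The right-hand column adds 90 days, or 120 at the end of the visit window, to the day of randomisation. Twenty-eight days is a ceiling, because some sections start the 4 weeks at the event or hospitalisation.

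**2. The plan's 91% power**

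Section 10.5 gives a 15-point difference, 320 evaluable (80 usual care, 240 intervention), two-sided 0.05, but no control rate. The 91% therefore cannot be reproduced outright. Solving the pooled two-proportion formula for the control rate gives 23.3% vs 8.3%:

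- Pooled rate = (80 × 0.233 + 240 × 0.083)/320 = 0.1205
- SE under the null = √[0.1205 × 0.8795 × (1/80 + 1/240)] = 0.0420
- SE under the alternative = √[0.233 × 0.767/80 + 0.083 × 0.917/240] = 0.0505
- Power = Φ[(0.15 − 1.96 × 0.0420)/0.0505] = 91%

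The unpooled formula reaches 91% at 18.8% vs 3.8%.

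**3. Assumptions for the illustration**

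The documents give no late-enrolment share, delay or hazard shape. I take a constant hazard, 14 or 28 days' delay, and shares of 12.5%, 25% and 50%. The 12.5% has a conditional anchor. At Bellevue, "Eligible patients will be called for approach after the letters are sent", and section 4.1 targets "150 participants within UMMHC and 50 within Bellevue Hospital". If that route means enrolment after discharge, Bellevue alone is 50/400 = 12.5%, before any CABG participants elsewhere.

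**4. One case in full: 25% late, 28 days, early stays captured**

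- Daily hazards: control −ln(1 − 0.233)/90 = 0.002947; intervention −ln(1 − 0.083)/90 = 0.000963
- Late intervention enrollee: 1 − exp[−(0.002947 × 28 + 0.000963 × 62)] = 13.3%
- Intervention arm overall: 0.75 × 8.3% + 0.25 × 13.3% = 9.5%; the control arm stays at 23.3%
- Difference 13.8 points; power 85%

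**5. All cases (power, %)**

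If early stays are not captured, both risks for late enrollees run over 90 − d days, where d is the delay. The last column captures early stays but halves the control hazard before randomisation in both arms, because enrollees must be well enough to attend and complete the 6MWT.

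| Late share | Delay (d) | Captured | Not captured | Captured, half hazard |
|---|---|---|---|---|
| 12.5% | 14 | 89.6 | 90.5 | 90.1 |
| 12.5% | 28 | 88.2 | 90.0 | 89.1 |
| 25% | 14 | 88.1 | 90.0 | 89.1 |
| 25% | 28 | 84.9 | 88.9 | 86.9 |
| 50% | 14 | 84.8 | 89.0 | 86.9 |
| 50% | 28 | 76.8 | 86.5 | 81.6 |

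Starting from 18.8% vs 3.8% with the unpooled formula moves the captured and not-captured figures by about one point at most. A front-loaded hazard (half of the 90-day hazard in the first 30 days) costs more: with capture, 81% at 25% late and 68% at 50% late, both at 28 days.

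**The case against.** The strongest reply is that the consequence is small. No arm is favoured, the primary endpoint is untouched, and at the one share with any anchor in the documents power moves from 91% to 88-90%. The 77% needs half the sample enrolled late, all at 28 days. That stands, and it limits the weight of the point. The power model is also a two-proportion test on back-solved rates, whereas section 10.4.3 plans logrank and Cox analyses, which can use follow-up from dropouts before censoring. The figures are therefore illustrative.

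A second reply is that section 4.2.2 already fixes the origin at discharge, so section 10.4.3 need not repeat it. If so, the pre-randomisation days are in the comparison by rule. A third is that one could simply count what the questionnaire collects, which gives late enrollees a full 3 months after randomisation. That is close to the right window, but it departs from the written definition and so confirms the mismatch.

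There is partial cover elsewhere. EHR review may find early stays within the participating systems. Adverse events after consent are recorded with onset times (section 8.3), and hospital stays are serious events (section 8.1.2), so many admission dates should already exist. But an outside stay before baseline is not asked about and could be missed, and the 6- and 12-month data do not repair the 3-month endpoint. A readmission before enrolment might itself become the qualifying hospitalisation and restart the clock; that is inference, but it would remove some early events.

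Finally, 3 months from discharge is a legitimate readmission measure. It suits a descriptive rate better than a randomised comparison.

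**Conclusion.** The concern holds. As defined, the 3-month readmission comparison includes days before randomisation for post-discharge enrollees, up to 28 of about 90 (31%), and the questionnaire covers a different period. This follows from the text and date arithmetic alone.

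The loss of power cannot be fixed from the documents. Under a constant hazard and rates back-solved from the stated 91%, it is about 1 to 6 points for late shares of 12.5-25% with early stays captured, and 1 to 2 points if they are not. Larger losses need a higher late share at the full 28 days, or a front-loaded hazard. It is dilution and ambiguity in one secondary endpoint, without bias toward an arm. The separate origin for death is a consistency remark, not a contradiction. The change should be made because it replaces a stated rule that misplaces the window, at little cost.

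**What to change.** - In sections 4.2.2 and 10.4.3, set time zero for the between-arm comparison at randomisation. Count the first overnight stay that begins after both randomisation and index discharge, through 3 months from randomisation, and likewise for 6 and 12 months.
- Align the 3-month questionnaire and the Week 8 and follow-up chart abstraction to that window, with admission dates, so that stays beyond 3 months reported at a late visit are not counted.
- Record stays between index discharge and randomisation as a baseline characteristic.
- Keep the 3-month post-discharge rate as a descriptive summary.

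The cost is wording, programming and, if not already recorded, an admission-date field. No visits or participants are added. The trade-off is that late enrollees are compared over later post-discharge days (up to about 28-118 rather than 0-90), which is why the discharge-based rate is kept.
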